8.2 Functional Assessment of Cancer Therapy-Vulvar (FACT-V)

HRQL will be measured by Functional Assessment of Cancer Therapy-Vulvar (FACT-V) [31], a validated and reliable FACT-V includes 15 vulvar cancer-specific items [38] captures dimensions of physical, social, emotional, and functional wellbeing, as well as pain/discomfort, discharge, odour, swelling, and urination. Coding of the 4-point Likert scale measure follows the FACT manual [39]. The FACT-V will be administered at baseline, 8 weeks, 6 months, and 12 months.

8.3 Lymphoedema Assessment

Lymphoedema will be self-assessed using validated questionnaires successfully used in our previous studies [16]. Where trained staff and appropriate equipment are available at sites, a subset of participants will have leg circumference measured as per the standard measurement protocol provided by the Australasian Lymphology Association, measuring every 10cm from the heel working proximally. The sum of leg circumferences will be calculated and compared to pre-treatment measurements. In clinical practice, an increase by 5% or more in those measurements is considered indicative of lymphoedema development, leading to initiation of treatment. If the increase is less than 5%, the participant is observed before initiating treatment. Also, when possible, the ImpediMed SOZO BIS device will be used to assess electrical impedance to extracellular fluid in the upper and lower limbs. As per the SOZO standard protocol, lymphoedema is indicated when the right or left ratio of impedance of the upper and lower limb exceeds one standard deviation of mean ratio from normative data. When this threshold is exceeded, referral to treatment will occur. Lymphoedema will be assessed at baseline, 8 weeks, 6 months, and 12 months after surgery.

8.3.1 Measurement Protocol for Lymphoedema Assessment

BIS refers to the process of sending non-detectable electrical currents ($n=256$), at a range of frequencies (3 kHz to 1000 kHz) through the body, allowing precise measurement and analysis of impedance to currents by extracellular fluid.

BIS measurements will be taken with the patient standing or, when patient is unstable or exceeds weight limits, sitting.

- Standing measurements are taken with the patient standing with legs apart, body weight distributed evenly on both feet, arms relaxed with elbows at their side and hands making contact with the electrodes.
- Sitting measures are taken with patient sitting fully upright, balanced in a non-metal chair. Body weight is to be distributed evenly on both hips, knees bent at a right angle, plus or minus 10 degrees.

For both sitting and standing measures, feet (no stockings/pantyhose or socks) are placed onto SOZO step, ensuring each foot is flat and in full contact with each electrode plate. Both hands are placed onto the SOZO touch with thumbs securely wrapped around the corners of each recess. Each hand must be flat and in full contact with each electrode plate.

All measurements take approximately 20 seconds and once complete and Cole plots are deemed acceptable data (R_0 , R_i , R_{inf} , fat mass (FM), fat-free mass (FFM), %FM, %FFM) will be stored for analysis. Lymphoedema status will be determined by using R_0 in the following equations:

Dominant side of the body:

predictor = $-18.41 + 5.58 (\text{arm } R_0/\text{leg } R_0) - 0.45 (\text{male}=1 | \text{female}=0) + 0.03 (\text{age}) + 0.24 (\text{BMI})$

probability = $\exp(\text{predictor}) / (1 + \exp(\text{predictor}))$

probability $> 0.045 =$ lymphedema

Non-dominant side of the body:

predictor = $-18.59 + 6.11 (\text{arm } R_0/\text{leg } R_0) - 0.44 (\text{male}=1 | \text{female}=0) + 0.02 (\text{age}) + 0.24 (\text{BMI})$

probability = $\exp(\text{predictor}) / (1 + \exp(\text{predictor}))$

probability $> 0.042 =$ lymphedema

BIS will be administered (if available and participant is on site) at baseline, 8 weeks, 6 months, and 12 months after surgery. These measures must be done at baseline, 6 months, and 12 months at least.

Where trained staff and appropriate equipment are available at sites, a subset of participants will have leg circumference measured as per the standard measurement protocol provided by the Australasian Lymphology Association, measuring every 10cm from the heel working proximally. The sum of leg circumferences will be calculated and compared to pre-treatment measurements. In clinical practice, an increase by 5% or more in those measurements is considered indicative of lymphoedema development, leading to initiation of treatment. If the increase is less than 5%, the participant is observed before initiating treatment. Lymphoedema will be assessed at baseline, 8 weeks, 6 months, and 12 months after surgery.

Participating Sites Only: Leg Circumference Measurements will be administered at baseline, 8 weeks, month 6 and month 12. These measures must be done Baseline, 6 months, and 12 months at a minimum.

8.4 Fear of Recurrence (FoR)

This four-item short-form (FCR-4) will be given to patients at 12 months post-surgery. It has been tested for its reliability and validity using classical psychometric and item response theory methods, and due to its brevity, poses low patient burden.

8.5 Decision-Making Tool

We will use the trial findings to develop a decision-making tool to support patient shared decision-making for groin USM or LND. This tool will be developed to align with the International Patient Decision Aid Standards (IPDAS) recommendations. It will include information about the probability of all important outcomes for each option including palpable groin node metastases and secondary endpoints such as lymphoedema and morbidity, and uncertainty, and support patients to consider their values and preferences for each outcome in order to achieve an informed decision.

In preliminary work, we have used a decision analysis approach to explicitly frame the treatment choice between groin USM and LND as a trade-off between the potential increased risk of nodal recurrence for USM versus the increased risk of lymphoedema and morbidity for LND using a decision tree. We used the decision tree to explore the impact of existing uncertainty about the probabilities of important outcomes and impact on health-related quality of life for each option on the expected value of USM versus LND. We will use the trial findings to build on the decision tree including explicit incorporation of patient preferences. We plan to use the decision tree approach to facilitate the co-development of an ANVU patient decision tool with consumer representatives, gynaecologists, surgeons, nurse consultants, and other stakeholders. Trial participants from Australian sites will be invited to opt in to receive an invitation to participate in a focus group for the development of the decision aid following the completion of their initial 12-month follow-up period.

Three focus groups will be formed, and each group will attend 4 x 2-hour sessions. Group 1 will comprise of 20 consumers previously treated for vulvar cancer. Group 2 will comprise of 20 certified gynaecological oncologists, nurse consultants, sonographers, and cancer service managers. Group 3

will comprise of 20 women randomised to the Intervention Group of ANVU. For equity, the sample will include rural/remote, younger, and older Australians to contribute important perspectives.

In Session 1 of the focus groups, we will present participants with practical information about US monitoring and LND options and a prototype decision tool based on our preliminary decision model data for the probabilities of groin node recurrence, lymphoedema, and QoL measures, summarised in an 'option grid' with graphics to communicate benefits, harms, and level of uncertainty. After trial completion, these data will be updated with actual trial results. Participants will assess the clinical, behavioural, cultural, and environmental fit of the proposed tool's components and processes with the lived experience of consumer or clinical decision making; refining these in Session 2, until consensus. In Session 3, guided by the Consolidated Framework for Implementation Research (CFIR) and IPDAS33, the groups will investigate five factors that might influence the implementation of the tool in practice; namely: (1) The evidence of the tool's quality and validity as perceived by stakeholders; (2) Consumer and clinical need; (3) Existing networks, cultures, desire for change and resources; (4) Key individuals and their capacity to advocate for or against the tool; and (5) Planning and engagement necessary to implement the tool. A draft implementation strategy associated patient information and decision-making resources will be developed from Session 3 data, which will be presented at Session 4 for revision and ratification.

The decision-making tool and its implementation strategy will be approved by all focus group participants (n=60). They will then be asked to complete the Acceptability, Appropriateness, and Feasibility of Intervention Measures (AAFIMs), with 12 items to assess whether respondents consider the tool and implementation strategy acceptable and appropriate. The AAFIMs and focus group data will be used to finalise the decision-making tool to support shared decision making and finalise an implementation strategy to enhance the uptake of the tool in the wider Australian and International setting.

9. Translational Research

In addition to the above, participants have the option to provide samples for use in future translational research. We will collect blood samples from participants who consent to be banked for the purpose of future molecular and biomarker research into vulvar cancer. Participants who receive standard groin LND will have blood collected at two time points: baseline (pre-operatively) and 8 weeks after surgery. For participants who have serial high-resolution groin USM, blood will be collected prior to surgery (baseline) and at each ultrasound scan (7-time points total). Participants can still participate in this study if they choose not to provide blood samples. Participants who consent to provide blood samples will be sent a blood collection request form for their preferred commercial pathology laboratory. Each participant will be asked to donate blood (up to 50 ml) at their convenience. Participants' blood samples will be collected for germline DNA (baseline only), circulating tumour DNA, plasma, and serum. For participants who have consented for the future use of blood samples, analyses will include examining circulating factors, such as extracellular vesicles and their contents.

Blood samples will be forwarded to a local pathology laboratory for processing and storage. Throughout the study, samples will be retrieved and stored at one or more of our central laboratories in Queensland, Australia, these include Mater Pathology and The University of Queensland Centre for Clinical Research. The blood samples will be assigned a unique code, which will be used in all analyses,

thus removing identifying information about the participant, and thereby protecting their privacy. Recruited participants will also be asked to provide FFPE tissue samples for use in future translational research. Tissue (vulvar tumour, lymph nodes) will be collected from all participants at the diagnostic biopsy procedure or during surgery (if applicable) as per standard clinical care.

These patients will be asked to participate in this project because, as part of their planned medical procedure, they will have their tumour biopsied or are undergoing surgery to have their tumour removed. Their scheduled biopsy or surgery is part of a medical treatment that they agreed upon with their doctor. During the procedure, cancer tissue will be removed, and their tissue blocks samples will be requested from pathology laboratories throughout the study. Analyses will include genotyping for HPV, and analysing biomarkers by immunohistochemistry, DNA sequencing, and other technologies.

10. Safety Reporting

The investigator is responsible for the detection and documentation of events meeting the criteria and definition of AE or a SAE as provided in this protocol. During the study, when there is a safety evaluation, the investigator or site staff will be responsible for detecting AEs and SAEs, as detailed in this section of the protocol.

The investigator/researcher must report all SAEs to QCGC Research within 24 hours of the site becoming aware of the SAE, in accordance with the study protocol and GCP guidelines.

10.1 Definition of an Adverse Event (AE)

An AE is any untoward medical occurrence in a patient, which does not necessarily have a causal relationship with this treatment. AE will be categorised using the CTCAE V5.0 and be collected for 12 months after surgery. An AE can be any unfavourable and unintended sign (including an abnormal laboratory finding), symptom, or disease (new or exacerbated) temporally associated with the use of a medicinal product, whether or not considered related to the medicinal product. For marketed medicinal products, this also includes failure to produce benefits (i.e. lack of efficacy), abuse or misuse.

Examples of an AE include:

- Exacerbation of a chronic or intermittent pre-existing condition including either an increase in frequency and/or intensity of the condition.
- New conditions detected or diagnosed after investigational product administration even though it may have been present prior to the start of the study.
- Signs, symptoms, or the clinical sequelae of a suspected interaction.
- Signs, symptoms, or the clinical sequelae of a suspected overdose of either investigational product or a concurrent medication (overdose per se should not be reported as an AE/SAE).
- Pre- or post-treatment events that occur as a result of protocol-mandated procedures (i.e. invasive procedures, modification of participants' previous therapeutic regimen).

Examples of an AE do not include:

- Medical or surgical procedures (e.g. endoscopy, appendectomy); the condition that leads to the procedure is an AE.

- Situations where an untoward medical occurrence did not occur (social and/or convenience admission to hospital).

10.2 Definition of a Serious Adverse Event (SAE)

A serious adverse event is any untoward medical occurrence that:

- results in death,
- is life threatening,

Note: The term 'life-threatening' in the definition of 'serious' refers to an event in which the participant was at risk of death at the time of the event. It does not refer to an event which hypothetically might have caused death if it were more severe.

- requires hospitalisation or prolongation of an existing hospitalisation,

Note: In general, hospitalisation signifies that the participant has been detained (usually involving at least an overnight stay) at the hospital or emergency ward for observation and/or treatment that would not have been appropriate in the physician's office or outpatient setting. Complications that occur during hospitalisation are AEs. If a complication results in prolonged hospitalisation or fulfils any other serious criteria, the event is serious. When in doubt as to whether 'hospitalisation' occurred or was necessary, the AE should be considered serious. Hospitalisation for elective treatment of a pre-existing condition that did not worsen from baseline is not considered an AE.

- results in disability/incapacity,

Note: The term disability means a substantial disruption of a person's ability to conduct normal life functions. This definition is not intended to include experiences of relatively minor medical significance such as uncomplicated headache, nausea, vomiting, diarrhoea, influenza, and accidental trauma (e.g. sprained ankle) which may interfere or prevent everyday life functions, but do not constitute a substantial disruption.

- is a congenital abnormality/birth defect, or

Medical and scientific judgement should be exercised in deciding whether reporting is appropriate in other situations, such as important medical events that may not be immediately life-threatening or result in death or hospitalisation but may jeopardise the participant or may require medical or surgical intervention to prevent one of the other outcomes listed in the above definition. These should also be considered serious. Examples of such events are invasive or malignant cancers, intensive treatment in an emergency room or at home for allergic bronchospasm, blood dyscrasias or convulsions that do not result in hospitalisation, or development of drug dependence or abuse.

- Any event deemed by the investigator as being a significant medical event.

SAEs will be categorised using the CTCAEs V5.0 and be collected for 6 months after surgery.

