7.5 Follow-Up (Visits 4-9)

All enrolled participants, irrespective of treatment group will be followed-up for 12 months. Participants without groin LND will be provided with medical imaging request forms to receive groin ultrasound examinations every 2 months. **Changes in ultrasound patterns from “normal” to “suspicious” will alert the gynae-oncologist and trigger further clinical action, such as groin LND and histological assessment of the groin nodes. Groin USM will not be offered to women who had a groin LND (IFL or SNB) as it is not standard practice for these patients.** If ultrasound scan surveillance following sentinel node biopsy is included in the standard care protocol at any of the study sites, participants randomised to lymph node dissection (LND) can undergo ultrasound scans as part of their standard care, though it is not mandatory for this study.

Participants will be assessed for local, regional, or distant recurrence, quality of life status, and treatment morbidity for 12 months. Data collected will include documentation of the status of disease, AEs, pain level, health status, quality of life and lymphoedema.

Participants randomised to serial groin USM will be seen every 3 months by a gynaecological oncologist or gynaecologist for clinical examination as per routine standard. Participants receiving standard groin LND (either SNB or LND) will be seen at 8 weeks, 3, 6, 9 and 12 months as per standard clinical practice. Follow up will be handed over to the treating gynaecological oncologist after 12 months.

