10.6.3 Exemptions from AE/SAE Reporting

Clinical Laboratory Abnormalities and Other Abnormal Assessments as AEs and SAEs:

Laboratory test value abnormalities will not be reported as AEs, unless there is an associated clinical condition for which the participant is given treatment, concomitant treatment is altered, or the event is considered a serious adverse event.

The investigator or designee will exercise their medical and scientific judgement in deciding whether abnormal laboratory findings, or other abnormal assessment is clinically significant.

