11.2.3 Morbidity of Intervention

Post-surgery, patients will be assessed daily until discharge from hospital. Perioperative outcomes including duration of surgery (time from skin incision to wound closure), length of hospital stay,

estimated intraoperative blood loss, requirements for blood transfusions, intraoperative complications, and crossovers (including the clinical necessity for a comprehensive LND) will be recorded. Intraoperative injuries, postoperative AEs and SAEs will be recorded according to the CTCAE V5.0, at predefined time points for up to 12 months. We will compare the incidence of (a) intraoperative; (b) postoperative; and (c) serious AEs at 8 weeks and 6 months and 12 months post-surgery.

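### No common rule says whether a groin node that leads to admission for dissection is an SAE, so the between-arm SAE comparison can be distorted, probably against ultrasound monitoring

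*Protocol*

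**What the plan says.** Section 10.1 does not count operations as adverse events, but it does count what prompts them: "Medical or surgical procedures (e.g. endoscopy, appendectomy); the condition that leads to the procedure is an AE". It also counts a condition first diagnosed after the intervention, even if it was there before the study began.

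Section 10.2 makes an event serious if it "requires hospitalisation or prolongation of an existing hospitalisation". Under important medical events, left to medical and scientific judgement, it adds: "Examples of such events are invasive or malignant cancers". Its only relevant exemption is: "Hospitalisation for elective treatment of a pre-existing condition that did not worsen from baseline is not considered an AE".

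Section 10.6.3 lists the reporting exemptions and deals only with laboratory and other abnormal assessments: "Laboratory test value abnormalities will not be reported as AEs", with conditions attached. It does not mention groin nodes or LND admissions.

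Section 7.5 says that a scan changing from normal to suspicious in the USM arm will "trigger further clinical action, such as groin LND and histological assessment of the groin nodes". Sections 6.5.3 and 10.6.5.1 leave the decision on LND to clinical judgement.

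Section 11.2.3, on morbidity, compares the incidence of intraoperative AEs, postoperative AEs and "c) serious AEs at 8 weeks and 6 months and 12 months post-surgery". Sections 10.2, 10.3 and 10.4 and the study schedule (section 16) collect SAEs for 6 months after surgery only.

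**The concern.** The two arms reach the same operation by different routes. In the LND arm the groin is dissected during the planned index admission. In the USM arm some women are dissected later, in a separate admission prompted by a node that was normal on the baseline scan. The SAE definition turns on unplanned admission and on worsening from baseline, so it picks up the second route more readily than the first.

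The SAE comparison would then mix two things: complications such as wound breakdown, cellulitis and readmission, and a count of women in whom monitoring did what it was designed to do. Lower morbidity is the second part of the trial's aim (section 5.2). A distorted SAE count in an open-label trial weakens one of the outcomes bearing on that aim.

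**Working it through.** **Step 1. Apply the wording to each arm.**

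| Rule | USM arm: node turns suspicious or positive, woman admitted for LND | LND arm: same occult node removed at index surgery |
|---|---|---|
| Operation itself (10.1) | Not an AE | Not an AE |
| Condition behind it (10.1) | AE | Could be read as a newly diagnosed condition; not stated |
| Requires hospitalisation (10.2) | Yes, a new admission | No, the admission was already planned |
| Elective exemption (10.2) | Fails: randomisation requires a negative baseline scan, and the trigger is a change from normal | Not needed |
| Malignant cancer example (10.2) | Applies if histology is positive, by judgement | Could apply to positive histology, by judgement |
| Exemption in 10.6.3 | None | None |

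The firm asymmetry is the hospitalisation row. The other rows are open to site judgement in both arms.

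**Step 2. Reproduce the pilot rate (section 3.4).** 3/32 = 0.09375 = 9.4%, as stated. The exact (Clopper-Pearson) 95% interval is 2.0% to 25.0%.

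**Step 3. Scale to the USM arm (about 120, section 6.4).** 120 × 0.09375 = 11.25, about 11 women over 12 months. The interval gives 120 × 0.020 = 2 to 120 × 0.250 = 30.

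**Step 4. Restrict to the SAE window.** The pilot text says all detections came within 12 months but does not split them at 6 months. The share inside the window is therefore assumed.

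| Assumed share by 6 months | Women of 120 | Percentage points |
|---|---|---|
| 25% | 2.8 | 2.3 |
| 50% | 5.6 | 4.7 |
| 75% | 8.4 | 7.0 |

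**Step 5. Possible offset in the LND arm (about 60).** At the same occult rate, 60 × 0.09375 = 5.6 women would have a positive node at planned surgery (interval 1 to 15). If sites reported none, there is no offset. If they reported all of them as malignant cancers, the offset would be 9.4 points, more than the USM effect in Step 4. The documents do not say which would happen.

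**Step 6. Illustration of the effect, with no LND-arm offset.** The protocol gives no background SAE rates, so these are assumptions. With background rate b and node-event share a, the observed USM rate is 1 − (1 − b)(1 − a). Power is for a two-sided 5% test of 60 versus 120.

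- Background 10% USM versus 20% LND: the true difference is −10.0 points, with power 0.46. At the 50% share, 1 − 0.90 × 0.9531 = 14.2%, so the observed difference is −5.8 points, with power 0.18. At 25% and 75% it is −7.9 and −3.7 points, with power 0.30 and 0.09.
- Background 15% in both arms: a spurious USM excess of 2.0, 4.0 or 6.0 points appears at the 25%, 50% or 75% share.

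**The case against.** A reader might infer that every delayed dissection or scan-detected node in the USM arm is an SAE by definition and that the LND arm scores zero. The documents do not support this, for four reasons.

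- The operation is excluded in section 10.1; only the condition can count.
- Nodes found at the month 8, 10 or 12 scans fall outside SAE collection.
- LND after a suspicious scan is a clinical decision, and the woman may continue monitoring.
- A positive node first found at upfront LND can be read under the same wording as a newly diagnosed condition and a malignant cancer. A full dissection after a sentinel node above 2 mm (section 6.5.2) can mean a second admission in the LND arm. Zero is an assumption, not a rule.

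A reader might also add the two histologically negative nodes in the pilot text and reach 5/32 (15.6%), or about 19 of 120. The pilot's accuracy figures point elsewhere. Sensitivity 100% (44–100%), specificity 97% (83–99%) and negative predictive value 100% (88–100%) match 3/3, 28/29 and 28/28 with Wilson intervals. That is 3 true positives, 1 false positive and 28 true negatives, 32 women in all. One false-positive woman does not make five events.

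It can also be said that crossovers and disease status are recorded separately, and that each AE carries a diagnosis and a causality assessment, so node events could be separated at analysis. AEs, lymphoedema, pain and patient-reported outcomes have their own comparisons, so the SAE count alone cannot hide a morbidity benefit. Prompt reporting of nodes that emerge under monitoring is a defensible safety choice.

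All of this stands and limits the point. It does not remove it. The protocol defines the SAE outcome and the comparison, nothing takes the triggering node out of the SAE count, and sites may class the same node differently.

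**Conclusion.** The point holds in a limited form. A node that becomes suspicious or positive after a normal baseline scan and leads to admission fits the SAE wording in the USM arm. The same node removed at index surgery does not meet the hospitalisation criterion. With no common rule, the comparison in section 11.2.3 can be distorted.

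The likely size is about 3 to 8 of 120 women (2 to 7 percentage points). This rests on the pilot rate, which is imprecise, on an assumed 25% to 75% of detections within 6 months, and on each detection leading to a reported SAE. The direction is probably against USM, because hospitalisation is the clearer criterion. It is not established, because reporting in the LND arm is unknown and could offset the effect.

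The outcome is secondary, and the primary Bayesian safety rule in section 11.1 is unaffected. The change is worth making because the outcome bears on the de-escalation claim and the correction is small.

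Separately, a 6-month SAE collection cannot supply a 12-month SAE comparison. The passages must be reconciled.

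**What to change.** - **Section 10.6.3:** state one rule for both arms. Groin-node events, and admissions for upfront, completion or delayed LND, are flagged as endpoint or pathway events. Keep prompt reporting of node events to the IDSMC; the flag governs analysis, not whether the committee hears of them.
- **Section 11.2.3:** make the between-arm morbidity comparison on SAEs excluding flagged events. Complications of any LND, prolonged stay and deaths stay in for both arms. Show all SAEs alongside, and tabulate crossover to LND separately.
- **Sections 10.2, 10.3, 10.4, 11.2.3 and 16:** make the SAE collection window and the times of the SAE comparison agree.

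The cost is a short paragraph, a sentence or two, one eCRF flag and one extra table.
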